### 1.4 Rucaparib

Rucaparib (also known as CO-338, formerly known as AG-14699 and/or PF-01367338) is a small molecule inhibitor of PARP being developed for cancer indications, to be used in conjunction with temozolomide, irinotecan, and other chemotherapeutic agents where PARP-related DNA repair may impede their maximum therapeutic effect. In addition, rucaparib is being investigated as a single agent in *BRCA1* and *BRCA2* patients with advanced/pretreated breast or ovarian neoplasia.

Results of studies with animal models suggest that rucaparib exposures that inhibit PARP will be associated with enhanced antitumor activity of temozolomide and other chemotherapeutic agents. Hence, the clinical program assessed bioactivity and safety in patients with malignancies, commonly treated with the selected chemotherapeutic agents. Based on the in vitro IC90 against the target, adjusted for protein binding, a sustained

plasma concentration of >5.9 ng/mL was projected to be needed in humans to inhibit PARP and enhance antitumor activity of chemotherapeutic agents. This target was reached at the 2 highest rucaparib doses (8 and 12 mg/m^2) in Part 1 of the Phase 1 study A4991002. Among the 3 patients who received the PID of 12 mg/m^2, concentrations of 10.6, 10.6, and 46.5 ng/mL, respectively, were observed 24 hours after rucaparib infusion on Day 1.

Non-clinical evaluation has demonstrated exquisite sensitivity of BRCA1 or BRCA2 homozygous cell lines, which is attributed to PARP inhibition alone, and provides a rationale for the clinical assessment of rucaparib as a single agent in patients with BRCA1 and BRCA2 deficient tumors.

Following administration of an IV dose of [14C]-labeled drug to intact rats, mean urine, and fecal recoveries were 33% and 61%, respectively, with a mean cumulative recovery of 95% of dose. Mean recovery of radioactivity in urine, bile, and feces from bile duct-cannulated rats was 49%, 31%, and 17%, respectively, with a mean cumulative recovery of 98%. Careful dose titration should be used in subjects with impaired renal and/or hepatic function. Following a single IV dose in rodents, dogs, or monkeys, mean systemic clearance was moderate to rapid, the apparent volume of distribution was large, and the terminal half-life was relatively short (t1/2: 2.8 hours in rats, 4.5 hours in dogs, 5.2 hours in monkeys).

## **1.5 Rucaparib + Chemotherapy**

In vitro studies in human tumor cells lines of rucaparib and similar compounds have shown that the combination of the PARP inhibitor with ionizing radiation, temozolomide, the topoisomerase I inhibitor camptothecin, and bleomycin increased the cytotoxicity of the DNA damaging agent. In the Phase 1 clinical study A4991002, 32 patients received at least 1 dose of rucaparib together with temozolomide. There were no deaths related to rucaparib. Two (6%) patients had nonfatal SAEs that were considered related to rucaparib. Many of the other events were related to the co-administered temozolomide and consistent with the known safety profile of temozolomide.

In the Phase 2 clinical study A4991005 of rucaparib and temozolomide forty-six patients were assigned to treatment and received at least 1 cycle of rucaparib (administered intravenously at a dose of  $12 \text{ mg/m}^2/\text{day}$  from Day 1 to 5 every 4 weeks) and Temozolomide (administered orally at a dose of  $200 \text{ mg/m}^2/\text{day}$  from Day 1 to 5 every 4 weeks). Eleven patients completed the study and 35 were discontinued early. All patients experienced treatment-related adverse events. The majority of CTC Grade 3 or 4 adverse events were myelotoxicities and occurred in cycle 1. The incidence of haematological toxicities appeared to be controlled by reducing the dose of temozolomide.

An ongoing phase I study is evaluating the safety, pharmacokinetic and pharmacodynamic of rucaparib administered with full combination doses of carboplatin, paclitaxel, cisplatin and pemetrexed.

## **1.6 Rucaparib (CO-338/AG-014699/PF-01367388) Starting Dose Rationale**

In the Phase 1 clinical study A4991002 the rucaparib Recommended Phase 2 Dose (RP2D) has been determined to be  $12 \text{ mg/m}^2/\text{day}$  for 5 days every 28 day cycle with full dose of Temozolomide.

Moreover from a pharmacokinetic point of view, whether a drug should be administered on a fixed dose or Body Surface Area (BSA) normalized dose depends on whether the pharmacokinetics of the drug changes with BSA. The effect of BSA on systemic exposure of rucaparib (AUC 0-24) was evaluated for this purpose. It is observed that the AUC 0-24 normalized for actual dose and the AUC (0-24) normalized for  $\text{mg/m}^2$  dose do not correlate with BSA. Furthermore, inter-subject variability is similar for actual dose normalized AUC (0-24) (53.9%) and  $\text{mg/m}^2$  dose normalized AUC (0-24) (54.1%). This suggests that rucaparib can be given either as a fixed dose or on a  $\text{mg/m}^2$  based dose.

The starting dose for rucaparib in the current study will be the fixed dose of 16 mg/day, lower than the 24 mg/day that would correspond to the "per square meter" RP2D of  $12 \text{ mg/m}^2/\text{day}$  determined in study A4991002. A single dose escalation to 30 mg/day will be allowed in patients without significant toxicity in cycle 1. In addition, as the

chemotherapy regimen being studied will be administered on a 3-week basis, the rucaparib schedule has been modified accordingly. rucaparib will thus be administered from Day 1 to Day 3 every 21 days. A similar dosing strategy has been employed in the planned/ongoing phase I trial evaluating rucaparib in combination with multiple chemotherapy regimens.

Complete information for rucaparib may be found in the current Investigator's Brochure.

## 1.7

### **Rucaparib (CO-338/AG-014699/PF-01367338) Oral Formulation**

The oral formulation of rucaparib contains the camsylate salt of the active agent rucaparib. All dosage strengths are express as the weight of free base rucaparib. Two strengths of oral rucaparib, 40 mg and 60 mg, are available as immediate release film coated tablets. The physical appearances of the tablets are unique in order to ensure proper identification. 40 mg rucaparib tablets are 9.5 mm round convex in shape, while 60 mg tablets are 15.4 mm x 8 mm oval in shape. In addition to active agent, tablets contain microcrystalline cellulose, sodium starch glycolate, dicalcium phosphate, and magnesium stearate. The cosmetic white film coating is Opadry II containing HPMC 2910, hypromellose 6cP, macrogol/PEG3350, triacetin, titanium dioxide, and lactose monohydrate.

In the on-going Phase I study of rucaparib in combination with chemotherapy, administration of the oral formulation is associated with average bioavailability is 30-40%, thus 100 mg is the estimated bioequivalent dose for the 30mg IV dose. Use of the oral dose during maintenance therapy will increase patient convenience and decrease the risk of infusion and/or access device related complications.

## 2.0

### **OBJECTIVES**

#### 2.1

#### **Primary Objective:**

- To evaluate 2-year disease-free survival (DFS), in patients with confirmed TNBC or ER/PR + HER2-, known BRCA1/2 mutations treated with single agent cisplatin and patients treated with cisplatin in combination with rucaparib following preoperative chemotherapy

#### 2.2

#### **Secondary Objectives:**

- To characterize the side effects and tolerability of cisplatin and cisplatin plus rucaparib in patients with residual disease following preoperative chemotherapy.
- To evaluate 1-year DFS.
- To determine 5-year overall survival.
- To collect limited pharmacokinetic data, in patients receiving study drug to compliment ongoing PK analyses in other trials with rucaparib.
- To collect archived tumor specimens and genomic DNA to explore potential correlates of PARP inhibition, recurrence and toxicity.
- To compare limited PK parameters between the IV and oral formulation of rucaparib

**3.0 ELIGIBILITY CRITERIA**

**3.1** Written informed consent and HIPAA authorization for release of personal health information.  
**NOTE:** HIPAA authorization may be included in the informed consent or obtained separately.

**3.2** Age  $\geq$  18 years at the time of consent.

**3.3** ECOG Performance Status 0 or 1 within 30 days prior to registration for protocol therapy.

**3.4** Women of childbearing potential and males must be willing to use an effective method of contraception from the time consent is signed until 4 weeks after treatment discontinuation.

**3.5** Women of childbearing potential must have a negative pregnancy test within 14 days prior to registration for protocol therapy.  
**NOTE:** Women are considered not of child bearing potential if they are surgically sterile (they have undergone a hysterectomy, bilateral tubal ligation, or bilateral oophorectomy) or they are postmenopausal.

**3.6** Women must not be breastfeeding.

**3.7** Must have histologically or cytologically confirmed triple negative (ER-/PR-/HER2-) invasive breast cancer, stage I-III at diagnosis (AJCC 6th edition) based on initial evaluation by clinical examination and/or breast imaging.

**NOTE: ER- and PR- should meet one of the following criteria:**

- Local Pathology report classifies them as negative
- Allred Score of 2 or below
- <5% weakly positive staining

Patients with ER+ and/or PR+ may enroll ONLY if they are known carriers of a deleterious mutation in BRCA1 or BRCA2. Patients with HER2+ tumors may not enroll regardless of BRCA status.

**3.8** Must have completed preoperative (neoadjuvant) chemotherapy.  
**NOTE:** Acceptable preoperative regimens include an anthracycline or a taxane, or both. Patients may NOT have received cisplatin as part of their neoadjuvant therapy regimen. Patients who received preoperative therapy as part of a clinical trial may enroll. No adjuvant chemotherapy after surgery other than that specified in this protocol is allowed. Adjuvant bisphosphonate use is allowed.

**3.9** Must have completed definitive resection of primary tumor. The last surgery for breast cancer must have been completed at least 14 days prior to registration for protocol therapy.

**NOTE:** Negative margins for both invasive and ductal carcinoma *in situ* (DCIS) are desirable, however patients with positive margins may enroll if the treatment team believes no further surgery is possible and patient has received radiotherapy. Patients with margins positive for lobular carcinoma *in situ* (LCIS) are eligible. Either mastectomy or breast conserving surgery (including lumpectomy or partial mastectomy) is acceptable. Sentinel node biopsy is allowed but axillary dissection is strongly encouraged in patients with lymph node involvement.

**3.10** Must have significant residual invasive disease at the time of definitive surgery following preoperative chemotherapy. Significant residual disease is defined *at least one of the following:*

- Miller-Payne response in the breast of 0-2. (Please refer to Study Procedure Manual[SPM]).
- Residual Cancer Burden (RBC) classification II or III.
- Residual carcinoma in one or more regional lymph nodes that would meet AJCC 6th edition criteria for N1 - N3 disease.
- Alternatively, if Miller-Payne or RCB grading is not available, the patient will be eligible if the pathology report indicates that the area of residual invasive disease in the breast measures at least 2 cm following preoperative therapy. The presence of DCIS without invasion does not qualify as residual disease in the breast.

**3.11** Whole breast radiotherapy is required for patients who underwent breast conserving therapy, including lumpectomy or partial mastectomy. Patients receiving adjuvant radiation therapy must have completed radiotherapy at least 14 days prior to registration for protocol therapy.

**NOTE:** Post-mastectomy radiotherapy is required for all patients with a primary tumor  $\geq$  5 cm or involvement of 4 or more lymph nodes. For patients with primary tumors  $< 5$  cm or with  $< 4$  involved lymph nodes, provision of post-mastectomy radiotherapy is at the discretion of the treating physician.

**3.12** Patients must enroll within 84 days of surgery (for those patients who do not require radiation) or within 84 days of completion of radiation when radiation is required

**3.13** No stage IV (metastatic) disease, however no specific staging studies are required in the absence of symptoms or physical exam findings that would suggest distant disease.

**3.14** No treatment with any investigational agent within 30 days prior to registration for protocol therapy.

**3.15** No history of chronic hepatitis B or C

**Laboratory values must be obtained within 14 days prior to registration.**

**3.16** Hemoglobin (Hgb)  $\geq$  9.0 g/dL

**3.17** Platelets  $\geq$  100 K/ mm^3

**3.18** Absolute neutrophil count (ANC)  $\geq$  1.5 K/mm^3

**3.19** Calculated creatinine clearance of  $\geq$  50 cc/min using the Cockcroft-Gault formula:

Males: 
$$\frac{(140 - \text{Age in years}) \times \text{Actual Body Weight in kg}}{72 \times \text{Serum Creatinine (mg/dL)}}$$

Females: Estimated creatinine clearance for males  $\times$  0.85

**3.20** Bilirubin  $\leq$  upper limit of normal (except in patients with documented Gilbert's disease, who must have a total bilirubin  $\leq$  3.0 mg/dL)

**3.21** Aspartate aminotransferase (AST, SGOT)  $\leq$  2.5  $\times$  ULN

**3.22** Alanine aminotransferase (ALT, SGPT)  $\leq$  2.5  $\times$  ULN

**3.23** Left ventricular ejection fraction within normal limits obtained within 30 days prior to registration for protocol therapy.

**3.24** Patients with an unstable angina or myocardial infarction within 12 months of study entry are excluded.

**3.25** No clinically significant infections as judged by the treating investigator.

**3.26** Must consent to allow submission of archived tumor tissue sample from definitive surgery.

**3.27** Must consent to collection of blood samples for PK analysis.

**3.28** No clinically significant arrhythmia or baseline ECG abnormalities in the opinion of the treating investigator.

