**Table 8: Dose Modifications for Toxicity Cycles 1-4 – Safety Run-in Cohorts, Arms A and B**

Event	Cisplatin	Rucaparib
Neutropenia (based on Day 1 CBC, no change required for interval neutropenia unless accompanied by fever)		
$\geq 1.5 \text{ K/mm}^3$	No change	No change
$< 1.5 \text{ K/mm}^3$	Hold until $\geq 1.5 \text{ K/mm}^3$ , resume based on timing of recovery: $\leq 1$ week – no change $>1$ but $\leq 3$ weeks - reduce dose 1 level for subsequent cycles $> 3$ weeks – discontinue therapy	Hold until $\geq 1.5 \text{ K/mm}^3$ , resume at the same dose upon recovery
Neutropenic Fever		
ANC $\leq 1000$ and fever $> 38.5$	Interrupt until resolved (ANC $>1000$ , fever $<38.5$ ), resume according to number of episodes: $1^{\text{st}}$ - no change, growth factor use mandatory for subsequent cycles. If growth factors were already used, reduce dose one level for all subsequent cycles. $2^{\text{nd}}$ - reduce dose one level $3^{\text{rd}}$ - discontinue therapy	Interrupt until resolved (ANC $>1000$ , fever $<38.5$ ), resume according to number of episodes: $1^{\text{st}}$ - no change $2^{\text{nd}}$ - reduce dose one level $3^{\text{rd}}$ - discontinue therapy
Thrombocytopenia (based on Day 1 CBC, no change required for interval thrombocytopenia)		
$\geq 100,000/\text{mm}^3$	No change	No change
$75-99,999/\text{mm}^3$	Hold until $\geq 100,000$ , resume based on timing of recovery: $\leq 1$ week – no change $>1$ but $\leq 3$ weeks - reduce dose 1 level for subsequent cycles $> 3$ weeks – discontinue therapy	Hold until $\geq 100,000/\text{mm}^3$ , resume at the same dose upon recovery
$<75,000$	Hold until $\geq 100,000$ , Resume with 1 level dose reduction for subsequent cycles. If $> 3$ weeks delay is required, discontinue therapy	Hold until $\geq 100,000/\text{mm}^3$ , resume at same dose upon recovery
Anemia		
Symptomatic anemia	No change. Transfuse as clinically indicated. NOTE: ESAs are not allowed due to restrictions on their use in the curative setting	
Hepatic		
$\geq \text{Grade 3}$	Delay until recovered to $\leq \text{Grade 2}$ , then resume at a one dose level reduction. If unable to resume therapy within 3 weeks, discontinue therapy	Delay until able to resume cisplatin, then resume at same dose
Nausea/Vomiting		

Grade $\geq$ 3 in spite of maximal antiemetics	Reduce dose one level for all subsequent cycles	No change
Renal		
Creatinine $\leq$ 1.5 x ULN	No change	No change

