$> 1.5$ but $\leq 2.0$ x ULN	Reduce dose one level and increase hydration	No change
$> 2.0$ ULN	Delay until recovered to $< 2.0$ ULN, then resume with one dose level reduction and increased hydration	Delay until able to resume cisplatin, then resume at same dose
Neurotoxicity on Day 1		
$\leq$ Grade 1	No change	No change
$\geq$ Grade 2	Delay until recovered to Grade 1, then resume with one dose level reduction. If unable to resume therapy within 3 weeks, discontinue therapy	Delay until able to resume cisplatin, then resume at same dose
Hearing Loss		
Grade 2	Cisplatin is well known to cause high-frequency hearing loss. Continued use of the drug does not always result in hearing loss, although it may do so. If grade 2 or worse hearing loss is noted, the patient should be presented with a discussion of the relative risks of hearing loss versus the potential benefit of continuing cisplatin therapy, and a decision made on the continuation of cisplatin.	No change
$\geq$ Grade 3	Discontinue Cisplatin	No change
Other clinically significant toxicities		
Grade 2	No change	No change
$\geq$ Grade 3	Delay until recovered to $\leq$ Grade 2, then resume at a one dose level reduction. If unable to resume therapy within 3 weeks, discontinue therapy	Delay until able to resume cisplatin, then resume at same dose

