## 7.2 ON TREATMENT

### 7.2.1 Day 1 of each cycle (within 3 days prior):

**Note: Cycle 1 Day 1 testing need not be repeated if completed within 7 days of starting protocol therapy.**

- Physical examination including
- weight, B/P and ECOG performance
- Platelets, ANC, Hgb
- Complete metabolic profile (CMP) including: serum chemistries (creatinine, glucose, total protein, blood urea nitrogen [BUN], total carbon dioxide [CO2], albumin, total bilirubin, alkaline phosphatase, and aspartate transaminase [AST] and alanine transaminase [ALT]) and electrolytes (total calcium, chloride, potassium, sodium)
- Calculated creatinine clearance
- ECGs will be done prior to each treatment cycle in the safety-run in cohorts and prior to cycle 3 of combined therapy in randomized portion of the study. Additional ECG monitoring should be considered at the treating physician's discretion, in patients who develop clinically significant electrolyte abnormalities
- Assessment of adverse events and concomitant medications
- PK levels: For patients enrolled in the safety-run-in portion of the study and Arm B - Mandatory plasma sample to be collected prior to infusion and 5 min (+/- 5 minutes) prior to the end of infusion on Cycle 1 Day 3 and Cycle 2 Day 3
- Optional whole blood sample (genomic DNA) to be collected on all patients at cycle 1 day1.
- Correlative studies: (See SPM for collection and shipping instructions).
  - Optional - tumor tissue submission from diagnosis

- Mandatory - tumor tissue submission from definitive surgery

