**10.2.7 Side Effects:**

**Nephrotoxicity:** Dose related and cumulative renal insufficiency is the major dose-limiting toxicity. Renal toxicity has been noted in 28-36% of patients treated with a single dose of 50 mg/m^2. It is first noted during the second week after a dose and is manifested by elevations in BUN and creatinine, serum uric acid, and/or a decrease in creatinine clearance.

Note: Renal toxicity becomes more prolonged and severe with repeated courses of the drug. Renal function must return to normal before another dose of cisplatin can be given.

**10.2.8 Ototoxicity:** Ototoxicity has been observed in up to 31% of patients treated with a single dose of cisplatin  $50 \text{ mg/m}^2$ , and is manifested by tinnitus and/or hearing loss in the high frequency range (4,000 to 8,000 Hz). Decreased ability to hear normal conversational tones may occur occasionally. Deafness after the initial dose of cisplatin has been reported rarely. Ototoxic effects may be more severe in children receiving cisplatin. Hearing loss can be unilateral or bilateral and tends to become more frequent and severe with repeated doses. Ototoxicity may be enhanced with prior or simultaneous cranial irradiation. It is unclear whether cisplatin-induced ototoxicity is reversible. Ototoxic effects may be related to the peak plasma concentration of cisplatin. Vestibular toxicity has also been reported. Ototoxicity may become more severe in patients being treated with other drugs with nephrotoxic potential. Patients should be questioned regarding any history of hearing deficit.

**10.2.9 Hematologic:** Myelosuppression occurs in 25% to 30% of patients treated with cisplatin. The nadirs in circulating platelets and leukocytes occur between days 18 to 23 (range 7.5 to 45) with most patients recovering by day 39 (range 13 to 62). Leukopenia and thrombocytopenia are more pronounced at higher doses ( $>50 \text{ mg/m}^2$ ). Anemia (decrease of 2 g hemoglobin/100 mL) occurs at approximately the same frequency and with the same timing as leukopenia and thrombocytopenia. Fever and infections have also been reported in patients with neutropenia. In addition to anemia secondary to myelosuppression, a Coombs' positive hemolytic anemia has been reported. In the presence of cisplatin hemolytic anemia, a further course of treatment may be accompanied by increased hemolysis, and this risk should be weighed by the Treating Physician.

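### The renal provisions for cisplatin re-dosing contradict each other: Table 8 permits doses that section 10.2.7 forbids, and the clearance recalculated before every cycle has no stated use

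*Combined protocol and SAP*

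**What the plan says.** Four places in the combined protocol and SAP deal with renal function and cisplatin.

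- **Entry, section 3.19.** Calculated creatinine clearance must be at least "50 cc/min using the Cockcroft-Gault formula", with actual body weight. The female value ("Females: Estimated creatinine clearance for males") carries a factor of 0.85.
- **On treatment, section 7.2.1 and the calendars in section 7.0.** "Calculated creatinine clearance" is among the assessments for "Day 1 of each cycle (within 3 days prior"). It also appears on Day 1 in all four calendars: safety run-in, Arm A, Arm B with IV maintenance, and Arm B with oral maintenance.
- **Dose modification, Table 8, renal rows.** The first row, "Creatinine $\leq$ 1.5 x ULN", leaves both drugs unchanged. Above 1.5 and up to 2.0 x ULN the cisplatin instruction is "Reduce dose one level and increase hydration". Above 2.0 x ULN cisplatin is delayed until creatinine is below 2.0 x ULN, "then resume with one dose level reduction and increased hydration". No row mentions clearance.
- **Drug information, section 10.2.7.** Renal toxicity is described as the major dose-limiting toxicity of cisplatin, "manifested by elevations in BUN and creatinine, serum uric acid, and/or a decrease in creatinine clearance". A note then says that no further cisplatin may be given until renal function is back to normal. It gives no value for normal and refers to neither Table 8 nor section 3.19.

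**The concern.** A site that follows Table 8 and a site that follows section 10.2.7 can treat the same Day 1 result in opposite ways, and each can cite the protocol. One gives cisplatin and the other withholds it. This affects both arms, since both receive cisplatin, and it concerns the toxicity that the protocol itself ranks first for this drug.

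The Day 1 clearance adds to the problem. The protocol judges renal fitness on that scale at entry and asks for it again before each cycle, but nothing in sections 5 and 6 says what to do with the result. Serum creatinine relative to ULN and Cockcroft-Gault clearance are different scales, so a patient can sit in the no-change row of Table 8 with a clearance below the entry requirement.

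The safety analysis is exposed as well. Table 2 counts a toxicity-related delay of more than 14 days in starting cycle 2 or 3 as a dose-limiting toxicity. Whether a renal delay reaches that length can depend on which of the two passages a site applied.

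**Working it through.** There is no statistical figure in the plan to reproduce here. The check has two parts.

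**1. The provisions side by side**

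| Day 1 serum creatinine | Table 8, cisplatin | Section 10.2.7 |
|---|---|---|
| Up to ULN | Unchanged | Depends on what normal means; clearance is among the signs named |
| Above ULN, up to 1.5 x ULN | Unchanged | Not normal on the creatinine scale: no dose |
| Above 1.5, up to 2.0 x ULN | One level lower, no wait for recovery | Not normal: no dose |
| Above 2.0 x ULN | Delay until below 2.0 x ULN, then one level lower | No dose until normal |

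ULN is by its name the upper limit of normal, so the conflict in rows 2 to 4 does not depend on how clearance is read. In row 1 the outcome turns on an undefined word. Section 3.19 accepts a clearance of 50 at entry, but nothing says whether 50 counts as normal under 10.2.7.

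**2. How far the two scales part**

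Formula for women, from section 3.19: clearance = (140 - age) x weight x 0.85 / (72 x creatinine). The documents give no laboratory ULN and no age or weight distribution. The assumptions are ages 45, 55 and 65; weights 50, 60, 70 and 80 kg; ULN 1.0, 1.1 and 1.2 mg/dL. Creatinine is set at 1.5 x ULN, the upper edge of the no-change row.

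Clearance (cc/min) at that edge, for the two outer ULN values:

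| Age | ULN | 50 kg | 60 kg | 70 kg | 80 kg |
|---|---|---|---|---|---|
| 45 | 1.0 | 37.4 | 44.9 | 52.3 | 59.8 |
| 55 | 1.0 | 33.4 | 40.1 | 46.8 | 53.5 |
| 65 | 1.0 | 29.5 | 35.4 | 41.3 | 47.2 |
| 45 | 1.2 | 31.2 | 37.4 | 43.6 | 49.8 |
| 55 | 1.2 | 27.9 | 33.4 | 39.0 | 44.6 |
| 65 | 1.2 | 24.6 | 29.5 | 34.4 | 39.4 |

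- Lowest: 75 x 50 x 0.85 / (72 x 1.8) = 24.6. Highest: 95 x 80 x 0.85 / (72 x 1.5) = 59.8.
- Combinations above 50: three at ULN 1.0 (age 45 at 70 and 80 kg, age 55 at 80 kg), one at ULN 1.1 (age 45 at 80 kg: 54.4), and none at ULN 1.2. The other 32 of 36 are below 50.
- General condition for a clearance below 50 at this edge: (140 - age) x weight < 50 x 72 x 1.5 x ULN / 0.85, which is about 6,353 at ULN 1.0 and 7,624 at ULN 1.2.
- Wider grid (ages 40-70, 50-90 kg, ULN 0.9-1.3): from 70 x 50 x 0.85 / (72 x 1.95) = 21.2 to 100 x 90 x 0.85 / (72 x 1.35) = 78.7.

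Such patients can be eligible. A woman of 60 years and 60 kg meets section 3.19 with creatinine up to 80 x 60 x 0.85 / (72 x 50) = 1.13 mg/dL. With ULN 1.0 she stays in the no-change row up to 1.5 mg/dL, where her clearance is 4,080 / 108 = 37.8.

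**The case against.** A reader might infer that no dosing rule takes account of clearance, that the Day 1 value can change no dose, and that a patient below the entry level therefore gets the next full dose with no action. The documents do not support this. Section 10.2.7 lists a fall in clearance among the signs of renal toxicity and then sets a condition on re-dosing. Section 5.1 ties changes in hydration to adequate renal function, and section 7.5 lets the physician stop treatment in the patient's interest. The absolute reading fails. These provisions do not close the gap, however: none gives a criterion, and the one in 10.2.7 conflicts with Table 8.

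It can also be said that entry limits in this protocol are not continuing limits. Hemoglobin must be at least 9.0 g/dL at entry, yet Table 8 keeps the dose unchanged even for symptomatic anemia. Bilirubin must be at or below ULN at entry, yet the hepatic row acts only from Grade 3. Other Day 1 measurements, such as albumin and glucose, have no dosing row either. This stands: a rule based on creatinine alone would be a legitimate choice, and nothing requires the floor in 3.19 to carry forward. It does not answer the conflict between Table 8 and 10.2.7.

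Section 10.2.7 could be read as background on side effects. But its note is worded as a condition for dosing, and no text ranks it below Table 8.

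Finally, the grid is chosen, its cells are equally weighted, and each sits at the extreme edge of a row. This also stands: 32 of 36 is not an estimate of how many patients are affected.

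**Conclusion.** The point holds as a contradiction between provisions. Table 8 permits cisplatin at creatinine values above ULN, at full dose up to 1.5 x ULN and reduced up to 2.0 x ULN, where section 10.2.7 withholds it until renal function is normal. This part needs no assumption beyond the meaning of ULN. In addition, clearance is required at entry and before each cycle without a statement of what it governs on treatment.

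The size of the divergence between the scales does rest on assumptions. At the edge of the no-change row, clearance is about 25-60 cc/min for women aged 45-65, 50-80 kg, ULN 1.0-1.2 mg/dL, and about 21-79 on the wider grid. It would be going too far to say that Table 8 leaves patients in general far below the entry floor: that is so for lighter or older women, while some younger or heavier women stay above 50. The documents allow no estimate of how often either occurs.

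**What to change.** Reconcile sections 3.19, 7.2.1, Table 8 and section 10.2.7 so that one consistent rule says which renal measure governs cisplatin on Day 1, what normal means if that condition is kept, and what the Day 1 clearance is for. If clearance is not meant to govern dosing, say so. The clinical team decides the measure, the threshold and the action; none is proposed here, and the entry floor should not be taken as an on-treatment trigger by default.

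The cost is one row or note in Table 8 and a matching edit in 10.2.7. No new data are needed, since both measures are already obtained each cycle. The small downside is that some patients who now pass on serum creatinine alone may have their dosing reviewed.
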